1. Myocardial rest/regadenoson stress perfusion PET study within 60 days
2. Rest LVEF (greater than or equal to 35%)
3. No change in symptoms or treatment between the PET and the MRI study
4. Willing to consent to the study
5. Male or female who is either post-menopausal, surgically sterile, or if has a childbearing potential, a negative pregnancy test within 2 days prior to the MRI study.
6. An estimated glomerular filtration rate completed within 6 months of participation.

Exclusion Criteria

1. Metallic implants, pacemaker, blood vessel clip (contra-indicated for MRI)
2. Patient size exceeds MRI bore/table limits: (Max body diameter > 70 cm, weight > 136 kg)
3. Second or third degree AV block
4. Sinus node dysfunction
5. Acute myocardial infarction (past 3 months)

6. Actively wheezing or with acute asthma or bronchospastic attacks requiring changes in therapy within the past 30 days
7. Patients that have experienced a previous hypersensitivity reaction thought to be related to regadenoson
8. Pregnant Women

STUDY PROCEDURES

Study staff will provide each subject with full and adequate verbal and written information using an IRB approved informed consent document, including the objective and procedures of the study and the possible risks involved before inclusion in the study. Informed consent will be obtained prior to performing any study-related procedures. If consent is gained, a copy of the executed consent form will be provided to the subject.

Following consent execution and prior to the MRI, the following screening measures will be performed and documented:

- Medical history, including surgeries and procedures;
- Medications, including herbal supplements and vitamins, will be reviewed;
- A MRI Patient Safety Screening questionnaire completed;
- Vital signs will be taken, to include heart rate, breathing rate, and blood pressure will be collected;
- An electrocardiogram will be performed;
- An intravenous catheter will be placed into the subject's arm;
- Females of child-bearing potential* will undergo a serum pregnancy test;
- If a creatinine blood test has not been done clinically in the last six months, one will be performed; and
- The qualifying, clinically-indicated cardiac PET procedure records will be collected.

** Females of childbearing potential are defined as not postmenopausal or surgically sterilized.*

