Consented subjects will be asked to undergo a rest/Lexiscan® (Regadenoson) stress cardiac MRI examination. For patients who do not have an estimated glomerular filtration rate on record within 6 months of participation, a creatinine will be drawn as part of the screening procedures. Patients with renal dysfunction (defined as an estimated glomerular filtration rate (GFR) < 60 mL/min/1.73m² within 6 months of participation) or a history of gadolinium contrast allergy or intolerance will participate in an abridged non-contrast protocol consisting of the localizer, functional and stress imaging sequences only, and no contrast will be administered.

There will be 40 subjects recruited into this study. 15 subjects will be recruited who had normal perfusion, normal LVEF and no WMA on a clinically indicated cardiac PET study. 25 subjects will be recruited into the ischemic cohort. Consented study participants will receive one dose of Lexiscan® (Regadenoson) while taking part in this protocol.

Ischemic Patient Population

The abnormal population will be selected from a group of patients with a clinically indicated myocardial perfusion PET study demonstrating reversible ischemic perfusion defect, a rest LVEF of $\geq 35\%$, and demonstrated WMA by quantitation, utilizing QPET's QGS analysis program

(Cedars Sinai Health System, Los Angeles, CA). A WMA will be defined as having a drop in LVEF from rest to stress and/or an extent of greater than or equal to 10% thickening and/or motion.

Myocardial perfusion rest/Regadenoson PET protocol

All PET studies will have been clinically indicated and performed prior to study participation. These studies will have been performed on a Biograph™-16 or Biograph™-64 PET/CT or Siemens ACCEL Dedicated PET system (Siemens Medical Solutions, Erlangen, Germany).

Biograph™-16 or Biograph™-64 PET/CT System

A low-dose CT image acquisition will have been acquired for attenuation correction. The resting perfusion images will have been acquired using 20-40 mCi of Rubidium-82, infused over 35 seconds. The ECG gated, list mode acquisition will have started prior to the start of the rubidium-82 infusion and continued for 7 minutes.

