With the subject in the same position, a single 0.4 mg dose of regadenoson in 5 mL saline will have been administered as a bolus over 10 seconds and immediately followed by a 5 mL saline flush. Following a 30 second delay, the stress images will have been acquired using 20-40 mCi of Rubidium-82 in ≤ 50 ml saline infused over <35 seconds. An ECG gated, list mode acquisition will have been started prior to the start of the Rb-82 infusion and continued for 7 minutes. A second low dose CT scan will have then been acquired for attenuation correction of the stress study.

Siemens ACCEL Dedicated PET

An infusion of 50 mCi of Rubidium-82 will be delivered 10 seconds after the beginning of the dynamic acquisition. First, a 150 second 2D dynamic acquisition will be acquired and followed by a 300 second 3D gated acquisition. Transition between 2D dynamic and the 3D gated acquisition was approximately 120 seconds.

With the subject in the same position, a single 0.4 mg dose of regadenoson in 5 mL saline will have been administered as a bolus over 10 seconds and immediately followed by a 5 mL saline flush. Following a 30 second delay, the stress images will have been acquired using 50 mCi of Rubidium-82 in ≤ 50 ml saline infused over <35 seconds. The 2D dynamic acquisition will have been followed by a 3D stress ECG gated acquisition.

Patients that meet these inclusion criteria will be discovered using a review of the St. Luke's nuclear database.

Cardiac MRI examination

All MRI studies will be conducted on either a 1.5-Tesla or 3.0 Tesla magnet. When subjects arrive, they will be consented and prepared for MRI scanning. The scanning technician will prepare the subject (screening, change of clothes, placement of positioning pillows, placement of hearing protection, vectorcardiogram leads, and an IV). Subjects will lie supine on the MRI table and then be advanced into the magnet bore. Of the subjects meeting inclusion/exclusion

criteria, those with a GFR < 60 mL/min/1.73m² or a history of gadolinium contrast allergy or intolerance will only perform the non-contrast portion of the following protocol, all others will follow the full protocol (Figure 2):

Non-Contrast CMR examination (Tagging at Rest, Stress)

- Localizers
- Pre-Contrast Rest Tagging Images:
 - Short Axis Cine (apex, mid, base)
 - Long Axis Cine (horizontal, vertical)
- Inject Regadenoson
- Pre-Contrast Stress Tagged:
 - Short Axis Cine (apex, mid, base)
 - Long Axis Cine (horizontal, vertical)

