***ONLY FOR PATIENTS WITH A DOCUMENTED GFR > 60 mL/min/1.73m² WITHIN 6 MONTHS OF PARTICIPATION**

[figure not shown]

Figure 2: CMR Protocol

The Lexiscan® (Regadenoson) will be administered by a clinical team of physicians, nurses, and clinical physiologists with extensive and daily experience with pharmacologic stress testing. The recommended intravenous dose of 5mL (0.4 mg regadenoson) will be administered as a rapid (approximately 10 seconds) injection into a peripheral vein immediately followed by a 5 mL saline flush. Subjects will be reversed using aminophylline if necessary, in the event of one or more of the following:

- a. ECG changes of ST depression >2mm or any significant ST elevation
- b. Onset of sustained second or third degree AV block
- c. Decreased systolic BP of >20mmHg on two (2) consecutive readings or BP > 240/110

- d. Wheezing
- e. Severe chest pain associated with ST depression of 2mm or greater.
- f. Signs of poor perfusion (pallor, cyanosis, and cold skin).
- g. Technical problems with monitoring equipment.
- h. Patient's request that on-going symptoms are severe.
- i. As deemed necessary by personnel administering the Lexiscan® (Regadenoson) stress test.

Aminophylline may be administered in doses ranging from 50 mg to 250 mg by slow intravenous injection (50 mg to 100 mg over 30-60 seconds) to attenuate severe and/or persistent adverse reactions to Lexiscan® (Regadenoson).

The contrast agent, MultiHance (gadobenate dimeglumine) will be administered by a clinical team of physicians, nurses and technologists with extensive and daily experience with contrast MRI. The recommended intravenous dose, 0.1 mmol/kg (0.2 mL/kg), of MultiHance will be administered as a rapid injection immediately followed by a 15 mL saline flush. Subjects with a calculated GFR < 60 mL/min/1.73m² within 6 months of participation or have a history of gadolinium contrast allergy or intolerance will not receive contrast.

DATA ANALYSIS

The measurement of PET function LVEF will be performed using the industry standard QPET analysis program (Cedars Sinai Health System, Los Angeles, CA). Absolute myocardial perfusion and flow will be measured using the ImagenQ quantitation package (CVIT, Kansas City MO).

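### The only exclusion for prior regadenoson reactions stops at hypersensitivity, so some resolved serious non-allergic reactions to the same dose at PET do not bar the research dose

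*Combined protocol and SAP*

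**What the plan says.** Inclusion criterion 1 requires "Myocardial rest/regadenoson stress perfusion PET study within 60 days". The PET protocol gives the dose, identically for both scanner types: "a single 0.4 mg dose of regadenoson in 5 mL saline will have been administered as a bolus over 10 seconds". Under Study Procedures, "Consented study participants will receive one dose of Lexiscan" at the MRI, and the Cardiac MRI examination section specifies it: "The recommended intravenous dose of 5mL (0.4 mg regadenoson) will be administered as a rapid (approximately 10 seconds) injection".

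Exclusion 7 covers "Patients that have experienced a previous hypersensitivity reaction thought to be related to regadenoson". No other eligibility item names an earlier reaction to the drug. Inclusion 3 requires "No change in symptoms or treatment between the PET and the MRI study". Exclusions 3 to 6 concern AV block, sinus node dysfunction, recent infarction, and wheezing or bronchospasm.

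The screening list opens with "Following consent execution and prior to the MRI, the following screening measures will be performed and documented". Its last item is "The qualifying, clinically-indicated cardiac PET procedure records will be collected". It does not say what is looked for in those records.

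**The concern.** The PET dose was clinically indicated; the MRI dose is given for the study. By design, each subject has already been exposed to the same dose, so the best available evidence of individual tolerance is in a record that the study collects. The eligibility rule uses that evidence for one type of reaction only.

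The protocol recognises other types. Its list of reasons for aminophylline reversal includes ST shifts, sustained AV block, falling blood pressure, wheezing and poor perfusion. That list applies after the study dose. It does not ask whether the same thing happened at the previous one. For gadolinium the plan goes further: contrast is withheld after intolerance as well as allergy.

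What is at stake is subject safety. No endpoint, analysis or power figure depends on it.

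**Working it through.** No sample-size or error-rate formula applies, and the plan states no figure to reproduce. The check sets the criteria beside the reactions they might catch, with one comparison of look-back windows.

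**Exposure.** PET: 0.4 mg in 5 mL over 10 seconds. MRI: 0.4 mg in 5 mL over about 10 seconds. Planned subjects re-dosed: 15 normal + 25 ischemic = 40 of 40. This counts exposure, not harm.

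**Items that name a prior reaction to the drug.** 6 inclusion + 8 exclusion = 14 items; one, exclusion 7, does so.

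**Screening measures.** History, medications, MRI questionnaire, vital signs, ECG, IV catheter, pregnancy test, creatinine and PET records make 9. None states a check of how the PET dose was tolerated. Several of the nine could never contain one, so the count matters less than the two that could: the history and the PET records.

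**Windows.** Subjects are consented on arrival for the MRI, so I count all windows back from that day.

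| Reaction at the qualifying PET | Criterion | Barred? |
|---|---|---|
| Hypersensitivity | Exclusion 7 | Yes |
| Myocardial infarction | Exclusion 5, 3 months (about 90 days) | Always, since 90 > 60 |
| Bronchospasm | Exclusion 6, 30 days | In part: it needs current wheezing, or an attack that led to altered therapy |
| AV block, second or third degree | Exclusion 3, no time frame | Unclear: it does not say whether transient stress-induced block counts |
| Sinus node dysfunction | Exclusion 4, no time frame | Unclear for a transient event |
| Any reaction that altered symptoms or treatment before the MRI | Inclusion 3, whole interval | Yes |
| Sustained symptomatic hypotension, resolved | None | No |

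For bronchospasm, exclusion 6 reaches back 30/60 = half of the PET window and leaves days 31 to 60 open. If treatment changed after such an attack, inclusion 3 bars the subject anyway. If it resolved with no change of treatment, neither item does.

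**What remains.** A serious non-allergic reaction at PET that resolved and left none of the listed conditions behind. Applied as written, the criteria admit that subject.

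**Other safeguards.** Adverse-event tracking (Secondary End-Point 2) concerns events from taking part in this study, so it does not reach back to the clinical PET dose. Aminophylline treats a reaction once it occurs; it does not settle whether to dose.

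**The case against.** The strongest reply is that the gap is mostly an unwritten decision rule. PET records are part of documented screening before the MRI. A medical history that covers procedures is taken. Exclusion 7 can hardly be applied without learning how earlier regadenoson was tolerated. The dose is given by physicians, nurses and physiologists who do pharmacologic stress testing daily, with reversal available on nine listed grounds, including staff discretion. Much of this stands: a reaction may well come to light, and an experienced team may decline to dose. But nothing written says what follows when the reaction found is serious and not allergic, and the stated rule would admit the subject.

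A reader might infer that nothing bars the dose after any serious reaction other than hypersensitivity. The documents do not support that: exclusion 5 always bars an infarction at the qualifying PET, and inclusion 3 and exclusions 3, 4 and 6 bar some other reactions. A reader might also infer that the PET records go unread. The text does not say so; it only fails to state a tolerance check.

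It is also fair to object that excluding every severe reaction that needed aminophylline would be a poor remedy. Severe chest pain with ST depression of 2 mm or more is itself a reversal trigger, so such a rule would remove the subjects the ischemic cohort is meant to study. The fix below avoids this.

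**Conclusion.** The point holds in a limited form. No criterion directed at earlier regadenoson reactions goes beyond hypersensitivity, and the remaining criteria catch only some serious reactions. A subject with a resolved serious non-allergic reaction at PET is eligible for a second, research-only dose of the same size.

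The number affected cannot be estimated, because the documents give neither a rate of such reactions nor a risk of recurrence. It is probably small. That all 40 subjects are re-dosed does not mean that 40 are at raised risk.

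The conclusion rests on two assumptions. First, a reaction that resolved is not itself counted as a change in symptoms under inclusion 3; if the sponsor reads that item more widely, the gap narrows. Second, the absence of a rule is shown only for the public text as supplied, from which the consent pages and some other pages were removed. The change is worth making because it closes a safety gap at little cost.

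**What to change.** Reword exclusion 7 to: *hypersensitivity or other serious non-ischemic reaction thought to be related to regadenoson (for example sustained symptomatic hypotension, bronchospasm, or sustained high-degree AV block)*.

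Change the last screening item so that, before MRI dosing, a physician on the stress team reviews the collected PET stress record for tolerance and documents the decision to dose.

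State that ischemic responses (ST change or chest pain, with or without aminophylline) prompt this review and do not exclude automatically, so that the ischemic cohort is not selected toward milder disease. Treat aminophylline use alone in the same way, since the protocol also allows reversal for equipment problems.

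Cost: about 40 short reviews, one per subject, plus one for each candidate reviewed and not dosed, using records already collected. A few candidates may be lost.

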***ONLY FOR PATIENTS WITH A DOCUMENTED GFR > 60 mL/min/1.73m² WITHIN 6 MONTHS OF PARTICIPATION**

[figure not shown]

Figure 2: CMR Protocol

The Lexiscan® (Regadenoson) will be administered by a clinical team of physicians, nurses, and clinical physiologists with extensive and daily experience with pharmacologic stress testing. The recommended intravenous dose of 5mL (0.4 mg regadenoson) will be administered as a rapid (approximately 10 seconds) injection into a peripheral vein immediately followed by a 5 mL saline flush. Subjects will be reversed using aminophylline if necessary, in the event of one or more of the following:

- a. ECG changes of ST depression >2mm or any significant ST elevation
- b. Onset of sustained second or third degree AV block
- c. Decreased systolic BP of >20mmHg on two (2) consecutive readings or BP > 240/110

- d. Wheezing
- e. Severe chest pain associated with ST depression of 2mm or greater.
- f. Signs of poor perfusion (pallor, cyanosis, and cold skin).
- g. Technical problems with monitoring equipment.
- h. Patient's request that on-going symptoms are severe.
- i. As deemed necessary by personnel administering the Lexiscan® (Regadenoson) stress test.

Aminophylline may be administered in doses ranging from 50 mg to 250 mg by slow intravenous injection (50 mg to 100 mg over 30-60 seconds) to attenuate severe and/or persistent adverse reactions to Lexiscan® (Regadenoson).

The contrast agent, MultiHance (gadobenate dimeglumine) will be administered by a clinical team of physicians, nurses and technologists with extensive and daily experience with contrast MRI. The recommended intravenous dose, 0.1 mmol/kg (0.2 mL/kg), of MultiHance will be administered as a rapid injection immediately followed by a 15 mL saline flush. Subjects with a calculated GFR < 60 mL/min/1.73m² within 6 months of participation or have a history of gadolinium contrast allergy or intolerance will not receive contrast.

DATA ANALYSIS

The measurement of PET function LVEF will be performed using the industry standard QPET analysis program (Cedars Sinai Health System, Los Angeles, CA). Absolute myocardial perfusion and flow will be measured using the ImagenQ quantitation package (CVIT, Kansas City MO).

Volumetric data and late gadolinium enhancement post-processing will be performed on an AW workstation using ReportCard v4 software (General Electric). Tagged images will be post-processed for strain and displacement (ΔR and $\Delta\theta$) measurements using the HARP® tagging analysis software package (Diagnosoft) or a similar industry standard software package.

Primary End-Point Analysis:

For each patient group, every segment of the myocardium will be classified as normal, reversible, or non-reversible based on the PET perfusion data. Then for each segment category the radial strain (ΔR) and rotational displacement ($\Delta\theta$) will be calculated using the HARP® software package (Diagnosoft). These values will be determined from tagged cine images obtained in three short axis (apical, mid, and basal) views of the left ventricle obtained during regadenoson induced stress and rest (or difference in stress values). Comparisons will be made using ANOVA and standard t-test methods.

1. For Primary End-Point 1 we will compare the radial strain (ΔR) and rotational displacement ($\Delta\theta$) of normal and abnormal segments *between the defined ischemic and normal patient groups*.
2. For Primary End-Point 2 we will compare radial strain (ΔR) and rotational displacement ($\Delta\theta$) at rest and stress *between abnormal and normal segment classifications*.

Secondary End-Point 1

The secondary end-points of this study will be analyzed using regression analysis to determine the relationships between radial strain (ΔR), rotational displacement ($\Delta\theta$), regional flow reserve, and the degree of transmurality (TEI) as defined by the presence of delayed gadolinium enhancement.

Secondary End-Point 2

Adverse events will be recorded on an Adverse Event log. This log will track:

1. Description of event
2. Start and stop time of event
3. Severity of event
4. Likelihood that the event is related to the study drug
5. Relationship of event to other test procedures
6. Any treatment actions taken
7. The final outcome

Although serious adverse events are not expected, serious adverse events will be reported to the IRB.

Powering Calculation

The patient to patient variability of normal resting LVEF is 5.3% (3). For the normal patients, there is an expected increase in ejection fraction of 8% (3). For ischemic patients, we have defined a change in ejection fraction of 2% as being significant. The net change would be a 10% change in difference in ejection fraction between the control (normal) and the ischemic groups.

If we assume cylindrical geometry, this would imply a roughly 5.6% change in the radius of the myocardium would result in a change in ejection fraction of 10% (assuming a resting LVEF of 55). Based on (3), this would give a Cohen's d of 1.06 and a total of 16 patients per group. However, given the need to explore the abnormal arm of the study, can obtain a similar power of 0.8 using an unequal population sizes of 13 (normal) and 22 (abnormal). We anticipate approximately 15% of patients that may not achieve sufficient quality of data would yield population of 15 normal subjects and 25 ischemic subjects to achieve the 0.8 power.

RESEARCH ENVIRONMENT

ASPIRE Foundation

Study funding will be provided by Astellas to the sponsor, the ASPIRE Foundation. The ASPIRE Foundation is a not-for-profit, non-invasive, imaging-based foundation dedicated to furthering knowledge about the role of imaging in improving patient outcomes. The ASPIRE Foundation is a joint venture between Saint Luke's Cardiovascular Consultants, the Mid America Heart Institute, and Cardiovascular Imaging Technologies. The ASPIRE Foundation will subcontract with Cardiovascular Imaging Technologies for staff to conduct its trials. Only CVIT study-

specific staff (Co-PIs: Drs. [name] and [name]; Sub-PIs: Drs. [name] and [name]; and Study Coordinators: [name] and [name]) will have access to patient data.

Saint-Luke's Cardiovascular Consultants

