Cardiac magnetic resonance (CMR) imaging is increasingly being used in the assessment of regional and global left ventricular function at rest and during vasodilator stress (16-18). CMR has many important technical advantages including a higher spatial resolution than PET or SPECT, improved tissue characterization (both with and without contrast), and superior repeatability and endocardial definition (including functional assessment) over echocardiography. Its power of tissue characterization is particularly highlighted with the use of late gadolinium enhancement (LGE) and its excellent spatial correlation with infarction, necrosis, and fibrosis (19). With respect to wall motion, myocardial strain imaging with CMR uses magnetic saturation "tag" lines (figure 1) to aid in qualifying and quantifying wall motion, is superior to echo-based strain techniques, and has been demonstrated to correlate well with LVEF (20-23).

At this time, there is ample evidence that vasodilator stress induces functional changes (4-7,9,11,12); however, without an understanding of the etiology of this process, its value in patient management is limited. In order to use functional changes induced by vasodilator stress, it is necessary to first understand the relationship between functional and perfusion abnormalities, local strain and fibrotic burden.

It is the intent of this research to quantify the effects of regadenoson on myocardial function and contraction in the presence of CAD. We are proposing a CMR protocol to evaluate myocardial viability and function, with CMR tagging, on a segment-based approach. We plan to evaluate correlations in wall motion changes (ie. - myocardial radial strain (ΔR) and/or displacement ($\Delta\theta$)) during regadenoson stress and correlate with areas of myocardial infarction (late gadolinium enhancement on CMR), areas with identified perfusion defect (on PET), and a change in LVEF magnitude (on both PET and CMR).

Figure 1: Tagged short axis cine view of the left ventricle (left panel) and late gadolinium enhancement image (right panel) showing a near transmural infarction of the septal wall.

HYPOTHESIS

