The hypothesis of this study is that in a population with a demonstrated perfusion defect and WMA (measured by Rb-82 PET), regadenoson stimulates changes in ventricular mechanics (radial strain and rotational displacement) and LVEF associated with the degree of ischemic or fibrotic burden. Additionally, these changes may be different for normal, ischemic, and infarcted myocardium and will be compared between a high-risk population and a cohort of low-likelihood normals.

PRIMARY END-POINTS

For each patient group, every segment of the myocardium will be classified as normal, reversible, or non-reversible based on the PET perfusion data. Then for each segment category the radial strain (ΔR) and rotational displacement ($\Delta\theta$) will be calculated using an industry

standard CMR software package (current plans are to use HARP®, Diagnosoft, Morrisville, NC, though another package may be used). These values will be determined from tagged cine images obtained in three short axis (apical, mid, and basal) views of the left ventricle obtained during regadenoson induced stress and at rest (or difference in stress values).

1. Primary End-Point 1 of this study is to determine if there is a measurable difference in the strain (ΔR) and/or displacement ($\Delta\theta$) of normal and abnormal segments between the defined ischemic and normal patient groups.
2. Primary End-Point 2 of this study is to determine if there are measurable differences in the strain (ΔR) and/or displacement ($\Delta\theta$) between segment classifications (normal, reversible, and non-reversible perfusion defects).

SECONDARY END-POINTS

Secondary end-points will be determined from tagged cine images obtained in three short axes (apical, mid, and basal) views of the left ventricle obtained during regadenoson induced stress and at rest (or difference in stress values).

1. Secondary End-Point 1 of this study is to determine the strain (ΔR) and/or displacement ($\Delta\theta$) scores correlate with flow reserve as measured by PET and/or transmural extent of infarction (TEI) indicated by Late Gadolinium Enhancement (LGE).
2. Secondary End-Point 2 of this study is to track any adverse events as a result of participation in this study.

STUDY DESIGN

Subjects who have had a clinically indicated, ECG-gated, Rb-82 myocardial perfusion PET study will be recruited for participation. Specific inclusion/exclusion criteria are:

Inclusion Criteria

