- Reverse Patient with aminophylline (if necessary)

*Late Gadolinium Enhancement to assess infarcted and fibrotic tissue:

- Injection of gadolinium contrast agent
- Delay of at least 8-15 minutes from injection
- Cine IR TI Scout
- LGE Short Axis(apex, mid, and base)
- LGE Long Axis(horizontal and vertical)

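### Both primary end-points class segments from PET perfusion alone, so scar can sit in the normal and reversible classes; pre-specify a PET-by-LGE analysis in patients who receive contrast

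*Combined protocol and SAP*

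**What the plan says.** Under PRIMARY END-POINTS, and again under DATA ANALYSIS (Primary End-Point Analysis), "every segment of the myocardium will be classified as normal, reversible, or non-reversible based on the PET perfusion data". Radial strain and rotational displacement are then compared by ANOVA and t-tests. End-Point 1 compares segments across the ischemic and normal patient groups. End-Point 2 compares segment classes. It names three classes under PRIMARY END-POINTS, but the analysis text describes the comparison as "between abnormal and normal segment classifications".

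Other parts of the protocol give LGE a distinct role:

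- The HYPOTHESIS section says "these changes may be different for normal, ischemic, and infarcted myocardium".
- The background on cardiac magnetic resonance (CMR) credits CMR with "a higher spatial resolution than PET or SPECT, improved tissue characterization (both with and without contrast" and LGE with "excellent spatial correlation with infarction, necrosis, and fibrosis". It pairs each modality with a tissue state: "areas of myocardial infarction (late gadolinium enhancement on CMR), areas with identified perfusion defect (on PET".
- The Cardiac MRI examination section schedules "Late Gadolinium Enhancement to assess infarcted and fibrotic tissue" for patients eligible for contrast.
- The analysis plan uses LGE only in Secondary End-Point 1, a regression relating strain and displacement to flow reserve and transmural extent of infarction (TEI).

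The exclusion criteria rule out acute infarction within the past 3 months only. Both cohorts are defined on PET findings, with no LGE criterion.

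**The concern.** The hypothesis needs ischemic and infarcted tissue to be told apart, and the plan's own marker of infarction plays no part in forming the primary classes. An older infarct does not exclude a patient. Nothing in the class definitions keeps a segment with scar out of the reversible class, or out of the normal class if its perfusion reads as normal.

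A strain deficit in reversible segments could then reflect regadenoson-induced ischemia, pre-existing scar, or both. End-Point 1 is exposed in the same way, because PET-normal segments of ischemic patients may contain scar. The End-Point 2 analysis wording adds to the difficulty: read literally, abnormal versus normal pools reversible with non-reversible segments. The trial could report a class difference and still be unable to say which tissue state produced it.

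**Working it through.** **The plan's own figure.** The plan gives no figure on scar by PET class. The nearest quantity is the Cohen's d of 1.06 in the Powering Calculation, which 5.6/5.3 = 1.057 reproduces. With a two-sided 5% level (assumed, since none is stated), the noncentral t gives 15 per group for 0.80 power, against 16 stated, and power 0.837 at 13 and 22. The present point changes none of these. The 1.06 serves below only as a yardstick: it derives from ejection fraction and a radius change in patients, not from segment strain.

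**Side-by-side reading.**

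| Element | Hypothesis and background | Primary analysis |
|---|---|---|
| Tissue states | normal, ischemic, infarcted | normal, reversible, non-reversible |
| Marker of infarction | LGE | none |
| Marker of perfusion defect | PET | PET |
| Older infarct | eligible | no rule to split, exclude or adjust |

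**Illustration (all inputs assumed).** Let dI and dS be the true effects of ischemia and scar on strain, in SD, relative to healthy tissue. Let fR and fN be the scarred shares of the PET reversible and normal classes. If scar replaces the ischemia effect in a scarred segment:

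- reversible class = (1 − fR)·dI + fR·dS
- normal class = fN·dS
- observed contrast = (1 − fR)·dI + (fR − fN)·dS

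Assumed ranges: fR 0.10 to 0.50, fN 0 to 0.10, dS 0.5 to 2.0.

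| True dI | Smallest observed | Largest observed |
|---|---|---|
| 0 | fR = fN = 0.10: 0 + 0 = 0.00 | fR = 0.50, fN = 0, dS = 2.0: 0 + 0.50 × 2.0 = 1.00 |
| 0.5 | fR = fN = 0.10: 0.90 × 0.5 + 0 = 0.45 | same corner: 0.50 × 0.5 + 1.00 = 1.25 |
| 1.06 | fR = 0.50, fN = 0.10, dS = 0.5: 0.53 + 0.40 × 0.5 = 0.73 | same corner: 0.53 + 1.00 = 1.53 |

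If scar instead adds to ischemia, the contrast is dI + (fR − fN)·dS. For dI = 1.06 that runs from 1.06 + 0 = 1.06 to 1.06 + 0.50 × 2.0 = 2.06.

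Scar alone can thus mimic an effect, enlarge one or shrink one, depending on shares and effects that the documents do not give.

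**The case against.** The strongest defense is that PET matches the end-point as written. End-Point 2 is about perfusion-defect classes, the background assigns perfusion defect to PET, and nowhere does the plan equate a non-reversible segment with an infarct. Secondary End-Point 1 then relates strain to both flow reserve and TEI. In a mechanistic study of 40 subjects, placing LGE in the secondary analysis is a defensible choice. This stands as a reason to keep the PET classes primary. It does not supply the separation that the hypothesis asks for: the regression is not stated to include PET class, and it leaves the class contrasts as they were.

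A second defense is that strain is measured at rest and at stress, so a scar deficit equal in both cancels in a stress-minus-rest change. That stands in part. The plan leaves open whether rest and stress values or their difference will be analyzed. Even on the change scale, with dS = 0, scarred segments that do not respond would dilute the contrast to (1 − fR)·dI: from 0.90 × 1.06 = 0.95 down to 0.50 × 1.06 = 0.53 in the illustration.

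A reader might infer more than the text supports:

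- That scarred segments do enter the normal and reversible classes. The documents give no frequency; they show only that such segments can.
- That PET misses thin subendocardial scar. The background claims better spatial resolution for CMR generally and does not compare LGE with PET for scar detection.
- That LGE-based classes should replace the PET classes. That would remove non-contrast patients from a primary analysis planned on 13 and 22 patients, which is a real trade-off.
- That the bias can be judged against the 5.6% radius change in the Powering Calculation. That figure comes from ejection fraction under cylindrical geometry and is not shown to be on the scale of segment strain.

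**Conclusion.** The point holds in a limited form. The primary classes are formed without the plan's own marker of infarction, older infarcts are eligible, and no primary comparison splits or adjusts for LGE. A strain difference between PET classes therefore cannot be cleanly assigned to ischemia rather than scar.

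Size and direction cannot be fixed from the documents. The ranges shown illustrate what moderate scar shares could do; they are not estimates for this trial. The conclusion rests on two things: scar being possible in segments that PET calls normal or reversible, and the aim of separating ischemia from infarction that the hypothesis states. It does not make the PET-based end-points invalid as comparisons of perfusion classes. The remedy is an inexpensive addition, not a change of primary analysis.

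**What to change.** Keep the PET classes as the primary analysis in all patients. For patients who receive contrast, pre-specify:

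1. A segment-level cross-table of PET class (normal, reversible, non-reversible) by LGE (TEI 0 versus TEI above 0), shown by patient group.
2. A repeat of End-Points 1 and 2 in the 3 × 2 = 6 mutually exclusive and exhaustive cells of that table. The contrast of reversible/LGE-negative with normal/LGE-negative is the ischemia estimate for End-Point 2. For End-Point 1, the normal/LGE-negative segments of the two patient groups are compared, so that scar in PET-normal segments of ischemic patients does not enter.

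The same text should say whether End-Point 2 compares three classes or abnormal with normal.

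**Cost.** Analysis wording and some programming. Tagging and LGE are both acquired in apical, mid and basal short-axis views in one examination, and TEI is already needed for Secondary End-Point 1. No added scan, visit or patient is required.

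**Downside.** Patients on the non-contrast protocol (GFR below 60 mL/min/1.73m², or gadolinium allergy or intolerance) do not contribute. Their number is not given, and the remaining set is partly selected on renal function. Some cells may be too small for more than description.
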